The prognosis of patients with recurrent or refractory osteosarcoma remains poor, with 10-year overall survival rates around 20%. Given the continued poor prognosis in this group of patients, novel treatment strategies are needed. There are no standard chemotherapeutic agents or targeted therapies proven to prolong survival in recurrent osteosarcoma. Glycoprotein non-metastatic B (GPNMB) is a type I transmembrane glycoprotein that is normally expressed in a variety of cell types including osteoblasts and osteoclasts, dendritic cells, macrophages, hematopoietic cells, melanocytes and keratinocytes. Aberrant and over expression of GPNMB has been demonstrated in a variety of cancers including osteosarcoma. GPNMB is predominantly expressed on the cell surface of malignant cells, whereas in normal tissues it is generally restricted to intracellular compartments. This unique expression pattern makes GPNMB an attractive target for antibody drug conjugate (ADC) targeted therapy. CDX-011 is an ADC directed against GPNMB. It is comprised of a fully-human IgG2 monoclonal antibody (CR011) conjugated to the potent microtubule inhibitor, monomethyl auristatin E (MMAE), via a protease-sensitive valine-citrulline peptide linker and p-aminobenzoic acid (PABA) spacer. CDX-011 is theorized to exert its antitumor activity by selectively delivering the potent cytotoxin MMAE to GPNMB-expressing tumor cells. Pre-clinical data suggest that CDX-011 may have anti-tumor activity in osteosarcoma. In this Phase 2 study, eligible patients between the ages of 12 months and 50 years with unresected, recurrent or refractory osteosarcoma will receive CDX-011, administered once every 21 days for up to 14 months. Progression free survival and response to therapy will be assessed. In addition, the tolerability and pharmacokinetic (PK) disposition of CDX-011 will be evaluated.

EXPERIMENTAL DESIGN SCHEMA

*Glembatumumab vedotin will be given on Day 1 of each 21-day cycle

Note: Patients who undergo surgical resection of or radiation to any site of measurable disease prior to completion of the 6th cycle of therapy will be taken off protocol therapy.

1.0 GOALS AND OBJECTIVES (SCIENTIFIC AIMS)

1.1 Primary Aims

1.1.1 To estimate whether CDX-011 therapy either improves the disease control rate at 4 months in patients with recurrent measurable osteosarcoma as compared to an historical COG experience or produces an objective response rate in patients without previous eribulin treatment.

1.2 Secondary Aims

1.2.1 To assess the feasibility and toxicity profile of CDX-011 in patients with recurrent osteosarcoma.

1.2.2 To describe the pharmacokinetics of CDX-011 in adolescents and young adults with recurrent osteosarcoma enrolled at COG sites and COG Phase 1 Consortium sites only.

1.2.3 To determine if there is a relationship between tumor GPNMB expression by IHC and response to CDX-011 therapy.

1.2.4 To estimate, in the cohort of patients previously treated with eribulin, the proportion who will experience disease progression during the first 4 months of CDX-011 therapy and the proportion of patients who experience a RECIST-defined complete or partial response.

2.0 BACKGROUND

2.1 Introduction/Rationale for Development

The outcome of patients with newly diagnosed, localized osteosarcoma improved following the addition of multi-agent chemotherapy to complete surgical resection.^{1,2} Current results in contemporary cooperative group studies reveal 3-year event-free survival (EFS) ranging between 50-75%.³⁻⁶ Cisplatin^{7,8} and doxorubicin^{9,10} are the most active agents, and standard chemotherapy includes the use of these two agents alone^{5,11} or in combination with high-dose methotrexate^{6,12} and/or ifosfamide.^{4,12-14} The prognosis is poor for the 30-40% of patients who develop recurrent disease,¹⁵ as well as for those with clinically detectable metastases at the time of initial diagnosis^{6,13,16} with 2-year survival rates of 20-30%.^{4,6,13,16-21}

The aggregate EFS for patients with recurrent osteosarcoma enrolled on seven closed Phase 2 studies from the COG or its predecessor groups is poor, with an overall 12% EFS at 4 months [95% CI: 6.0%-19%].

Due to the lack of progress seen in treatment of osteosarcoma over the past 25 years and overall poor prognosis for children, adolescents and young adults with recurrent or refractory osteosarcoma, novel treatment strategies are needed.

CDX-011 is an antibody drug conjugate (ADC) directed against Glycoprotein non-metastatic B. The preclinical data that establishes the rationale for proceeding with a Phase 2 evaluation in patients with relapsed or refractory osteosarcoma is described below.

Glycoprotein non-metastatic B (GPNMB) as a therapeutic target: GPNMB (also known as osteoactivin, dendritic cell-heparin integrin ligand, or hematopoietic growth factor inducible neurokinin-1 type) is a type I transmembrane glycoprotein^{[22-32](#)} that is normally expressed in a variety of cell types including osteoblasts and osteoclasts, dendritic cells, macrophages, hematopoietic cells, melanocytes and keratinocytes.^{[22-25,28,32-36](#)} While its exact function in normal cells is not fully understood, it is thought to play a role in tissue repair, cellular adhesion, and regulation of cell growth and differentiation.^{[23,33-38](#)} Aberrant or overexpression of GPNMB has also been demonstrated in a variety of cancers including melanoma, breast cancer, glioma, hepatocellular carcinoma, and osteosarcoma.^{[23,24,26-29,31,32,39](#)} *In vitro* and *in vivo* studies have demonstrated a role for GPNMB in T cell activation, osteoblast development, osteoclast differentiation and fibroblast differentiation. GPNMB over expression was demonstrated to increase tumor invasiveness and metastasis by promoting angiogenesis and decreasing apoptosis in breast cancer, glioma and hepatocellular carcinoma cell lines.^{[23,25-30,32,33,40](#)} GPNMB is predominantly expressed on the surface of malignant cells, whereas in normal tissues it is generally restricted to intracellular compartments. This unique expression pattern makes GPNMB an attractive target for ADC targeted therapy.^{[25,27,32,39-42](#)}

CDX-011: CDX-011 consists of a fully-human IgG2 monoclonal antibody (CR011) conjugated to the potent microtubule inhibitor, monomethyl auristatin E (MMAE) via a protease-sensitive valine-citrulline peptide linker and p-aminobenzoic acid (PABA) spacer. CDX-011 is theorized to exert its antitumor activity by selectively delivering the potent cytotoxin MMAE to GPNMB-expressing tumor cells. After intravenous (IV) administration, CDX-011 binds to GPNMB on the surface of tumor cells. Lysosome internalization of the CDX-011-GPNMB complex leads to the proteolytic cleavage of the valine-citrulline linker and the release of free MMAE into the cytoplasm. Microtubule inhibition by MMAE leads to cell cycle arrest and subsequently tumor cell death.

Antitumor activity of CDX-011 has been demonstrated in xenograft models of melanoma, breast cancer, and osteosarcoma.^{[23,27,31,34,38,43,44](#)} Additionally, clinical efficacy was observed in adult breast cancer and melanoma trials, making CDX-011 an attractive agent for Phase 2 testing in patients with osteosarcoma. A positive result in this study in addition to the results of other planned studies of CDX-011 will help inform the design of future clinical trials for patients with osteosarcoma.

2.2 Preclinical Studies

The activity of CDX-011 in pediatric tumors was recently investigated through the Pediatric Preclinical Testing Program. GPNMB gene expression was evaluated in a variety of solid tumor and leukemia xenograft models. Given the consistent expression of GPNMB in the osteosarcoma xenografts, the *in vivo* anti-tumor activity was investigated in 6 female CB-17SC mice bearing osteosarcoma. The mice received 2.5 mg/kg of CDX-011 IV weekly for 3 doses, followed by 3 weeks of observation. Complete tumor responses were seen in 3/6 osteosarcoma xenografts. Of the 3 responding xenografts, 2 had the highest levels of GPNMB expression. The lowest GPNMB-expressing osteosarcoma xenograft had minimal response to CDX-011 treatment (Figure 1).^{[23,45](#)} GPNMB protein expression through immunohistochemistry and by enzyme-linked immunosorbent assay (ELISA) has

also been assessed in human osteosarcoma cell lines. Sixty-seven human osteosarcoma samples were tested and 92.5% of osteosarcoma samples expressed GPNMB. CDX-011 induced cytotoxic effects in 74% of osteosarcoma cell lines and GPNMB protein levels correlated with CDX-011 *in vitro* cytotoxicity.⁴⁶

[figure not shown]

Figure 1. CDX-011 *in vivo* objective response activity for osteosarcoma models. Kaplan-Meier curves for EFS (left), median relative tumor volume graphs (center), and individual tumor volume graphs (right) are shown for selected lines. Treated (black lines), statistical significance (P values) of the difference between treated and control groups are included.

2.3

In this trial a tumor sample to test for GPNMB expression by immunohistochemistry (IHC), similar to the previous breast cancer and melanoma clinical trials, will be required. This will allow us to determine if higher levels of GPNMB expression by IHC correlates with tumor response to CDX-011 in osteosarcoma patients.

2.4 Pediatric Studies

There are no data regarding the use of CDX-011 in children. Therefore, this trial will evaluate CDX-011 using a dosage and a schedule of administration that has been shown to be safe in patients with breast cancer and patients with melanoma. In order to assess the tolerability of this dose, 1.88 mg/kg rounded to 1.9 mg/kg, the first six children aged less than 18 years ('younger patients') who enroll on the trial will receive protocol therapy with close toxicity monitoring. Accrual of younger patients will temporarily be suspended after the sixth such patient is enrolled and these patients will be followed to ensure that there are not unanticipated toxicities. Accrual will resume at this dose if fewer than one-third of toxicity evaluable patients experience a DLT. We will continue to monitor closely for toxicities, as we do with all active COG Phase 2 trials. Enrollment of patients 18 years of age or older will continue during the evaluation of toxicity for younger patients. Pharmacokinetic studies are mandatory for the first 6 evaluable patients 14 years of age or less enrolled at any COG member institution. Consent for pharmacokinetic studies for any patient greater than 14 years of age and less than or equal to 21 years of age enrolled at any COG member institution is optional. PK sampling will not be sought for patients who are older than 21 years of age at the time of enrollment.

2.5 Dosing Rationale

CDX-011 will be administered intravenously at a dose of 1.9 mg/kg over 90 minutes on Day 1 of each 3 week cycle. The half-life is 40 hours. This dosing is based on the dosing guidelines used in the Phase 1/2 trial in patients with localized and advanced metastatic breast cancer and stage III or IV melanoma.

3.0 STUDY ENROLLMENT PROCEDURES AND PATIENT ELIGIBILITY

3.1 Study Enrollment

3.1.1 Patient Registration

Prior to enrollment on this study, patients must be assigned a COG patient ID number.

COG sites: This number is obtained via the COG Registry system once authorization for the release of protected health information (PHI) has been obtained. The COG patient ID number is used to identify the patient in all future interactions with COG. If you have problems with the registration, please refer to the online help.

Non-COG sites: Fax the patient registration information (demography) to the Cancer Trials Support Unit (CTSU) registrar at [name]. Sites may notify the registration office of an incoming fax by calling [name]; the office hours are 9:00 – 5:30 pm Eastern Time, Monday – Friday. The CTSU registrar will then register the patient within the COG system on behalf of the institution and obtain a COG patient ID number. The CTSU registrar will provide the COG patient ID number to the site which can then enroll the patient in the OPEN system.

A Biopathology Center (BPC) number will be assigned as part of the registration process. Each patient will be assigned only one BPC number per COG Patient ID. For additional information about the labeling of specimens please refer to the Pathology and/or Biology Guidelines in this protocol.

Please see [Appendix I](#) for detailed CTEP Registration Procedures for Investigators and Associates, and CTSU Registration Procedures including: how to download site registration documents; requirements for site registration, submission of regulatory documents and how to check your site's registration status.

3.1.2 IRB Approval

Sites must obtain IRB/REB approval for this protocol and submit IRB/REB approval and supporting documentation to the CTSU Regulatory Office before they can be approved to enroll patients. Allow 3 business days for processing. The submission must include a fax coversheet (or optional CTSU IRB Transmittal Sheet) and the IRB approval document(s). The CTSU IRB Certification Form may be submitted in lieu of the signed IRB approval letter. All CTSU forms can be located on the CTSU web page (<https://www.ctsu.org>). Any other regulatory documents needed for access to the study enrollment screens will be listed for the study on the CTSU Member's Website under the RSS Tab.

IRB/REB approval documents may be faxed ([name]), E-mailed ([contact]) or mailed to the CTSU Regulatory office.

When a site has a pending patient enrollment within the next 24 hours, this is considered a "Time of Need" registration. For Time of Need registrations, in addition to marking your submissions as 'URGENT' and faxing the regulatory documents, call the CTSU Regulatory Helpdesk at: [name]. For general (non-regulatory) questions call the CTSU General Helpdesk at: [name].

Study centers can check the status of their registration packets by querying the Regulatory Support System (RSS) site registration status page of the CTSU members' web site by entering credentials at <https://www.ctsu.org>. For sites under the CIRB initiative, IRB data will automatically load to RSS.

Note: Sites participating on the NCI CIRB initiative and accepting CIRB approval for the study are not required to submit separate IRB approval documentation to the CTSU Regulatory Office for initial, continuing or amendment review. This information will be provided to the CTSU Regulatory Office from the CIRB at the time the site's Signatory Institution accepts the CIRB approval. The Signatory site may be contacted by the CTSU Regulatory Office or asked to complete information verifying the participating institutions on the study. Other site registration requirements (ie, laboratory certifications, protocol-specific training certifications, or modality credentialing) must be submitted to the CTSU Regulatory Office or compliance communicated per protocol instructions.

3.1.3 Reservation Requirements

Prior to obtaining informed consent and enrolling a patient, a reservation must be made following the steps below. Reservations may be obtained 24 hours a day through the Oncology Patient Enrollment Network (OPEN) system.

Patient enrollment for this study will be facilitated using the Slot-Reservation System in conjunction with the Registration system in OPEN. Prior to discussing protocol entry with the patient, site staff must use the CTSU OPEN Slot

Reservation System to ensure that a slot on the protocol is available for the patient. Once a slot-reservation confirmation is obtained, site staff may then proceed to enroll the patient to this study.

If the study is active, a reservation can be made by following the steps below:

- 1) Log in to <https://open.ctsu.org/open/> using your CTEP IAM user name and password.
- 2) In order to make a reservation, the patient must have an OPEN patient number. Click on the 'Slot Reservation' tab to create an OPEN patient number, under 'Patients'.
- 3) Using the OPEN patient number 'RESERVE' a slot for that patient.
- 4) On the 'Create Slot Reservation' page, select the Protocol Number, enter the COG Patient ID, and choose the required stratum (if applicable) in order to obtain a reservation.

Refer to the 'SITE – Slot Reservation Quick Reference' guide posted under the 'Help' tab in OPEN for detailed instructions:

https://www.ctsu.org/readfile.aspx?fname=OPEN/OPEN_SlotReservation_QuickReference_SiteUserGuide_102612.pdf&ftype=PDF

3.1.4 Study Enrollment

Patient enrollment will be facilitated using the Oncology Patient Enrollment Network (OPEN). OPEN is a web-based registration system available on a 24/7 basis. To access OPEN, the site user must have an active CTEP-IAM account (check at <<https://eapps-ctep.nci.nih.gov/iam/index.jsp>>) and a 'Registrar' role on either the lead protocol organization (LPO) or participating organization roster.

All site staff will use OPEN to enroll patients to this study. It is integrated with the CTSU Enterprise System for regulatory and roster data and, upon enrollment, initializes the patient position in the Rave database. OPEN can be accessed at <https://open.ctsu.org> or from the OPEN tab on the CTSU members' side of the website at <https://www.ctsu.org>.

Prior to accessing OPEN, site staff should verify the following:

- All eligibility criteria have been met within the protocol stated timeframes.
- All patients have signed an appropriate consent form and HIPAA authorization form (if applicable).

Note: The OPEN system will provide the site with a printable confirmation of registration and treatment information. Please print this confirmation for your records.

Further instructional information is provided on the CTSU members' web site OPEN tab or within the OPEN URL (<https://open.ctsu.org>). For any additional questions contact the CTSU Help Desk at [name] or [contact].

3.1.5 Timing

Patients must be enrolled before treatment begins. The date protocol therapy is projected to start must be no later than **seven (7)** business days after the date of study enrollment. **Patients who are started on protocol therapy on a Phase 2 study prior to study enrollment will be considered ineligible.**

All clinical and laboratory studies to determine eligibility must be performed within 7 days prior to enrollment unless otherwise indicated in the eligibility section below.

Institutions are advised to plan ahead to ensure adequate and timely delivery of the investigational agent (see [Section 6.1](#) for details).

3.1.6 Participation in Biology Studies

In order to minimize the potential for non-compliance once enrolled, patients/guardians must be made aware that some of the biology research studies are mandatory and understand that a number of non-standard blood samples will be required.

3.1.7 Inclusion of Women and Minorities

Both men and women of all races and ethnic groups are eligible for this study.

3.2 Patient Eligibility Criteria

Important note: The eligibility criteria listed below are interpreted literally and cannot be waived. All clinical and laboratory data required for determining eligibility of a patient enrolled on this trial must be available in the patient's medical/research record which will serve as the source document for verification at the time of audit.

All clinical and laboratory studies to determine eligibility must be performed within 7 days prior to enrollment unless otherwise indicated. Laboratory values used to assess eligibility must be no older than seven (7) days at the start of therapy. Laboratory tests need not be repeated if therapy starts within seven (7) days of obtaining labs to assess eligibility. If a post-enrollment lab value is outside the limits of eligibility, or laboratory values are > 7 days old, then the following laboratory evaluations must be re-checked within 48 hours prior to initiating therapy: CBC with differential, bilirubin, ALT (SGPT) and serum creatinine. If the recheck is outside the limits of eligibility, the patient may not receive protocol therapy and will be considered off protocol therapy. Imaging studies, if applicable, must be obtained within 2 weeks prior to start of protocol therapy (repeat the tumor imaging if necessary).

See [Section 4.2.1](#) for required studies to be obtained prior to starting protocol therapy.

3.2.1 Age

Patients must be equal to or greater than 12 years of age but less than 50 years of age at the time of enrollment.

3.2.2 Diagnosis

3.2.2.1 Patients must have had histologic verification of osteosarcoma at original diagnosis or relapse.

3.2.2.2 Patients must have measurable disease according to RECIST 1.1 (see Section 10.2), and have relapsed or become refractory to conventional therapy.

3.2.3 Specimen Submission

Patient must have archival tumor specimen available for submission (see [Section 15.1](#)).

3.2.4 Performance Level

Patients must have a performance status corresponding to ECOG scores of 0, 1 or 2. Use Karnofsky for patients > 16 years of age and Lansky for patients ≤ 16 years of age. See

https://members.childrensoncologygroup.org/prot/reference_materials.asp under Standard Sections for Protocols.

3.2.5 Prior Therapy

Patients must have fully recovered from the acute toxic effects of all prior chemotherapy, immunotherapy, or radiotherapy prior to entering this study.

- a. Myelosuppressive chemotherapy: Must not have received within 2 weeks of entry onto this study (4 weeks if prior nitrosourea).
- b. Biologic (anti-neoplastic agent): At least 7 days since the completion of therapy with a biologic agent.
- c. Radiation therapy (RT): ≥ 2 weeks for local palliative RT (small port); ≥ 6 months must have elapsed if prior craniospinal RT or if $\geq 50\%$ radiation of pelvis; ≥ 6 weeks must have elapsed if other substantial BM radiation.
- d. Monoclonal antibodies: Must not have received any monoclonal based therapies within 4 weeks, and all other immunotherapy (tumor vaccine, cytokine, or growth factor given to control the cancer) within 2 weeks, prior to study enrollment.

Please see [Section 4.1.1](#) for the concomitant therapy restrictions for patients during treatment.

3.2.6 Organ Function Requirements

3.2.6.1 Adequate Bone Marrow Function Defined As:

- Peripheral absolute neutrophil count (ANC) $\geq 1000/\mu\text{L}$
- Platelet count $\geq 75,000/\mu\text{L}$ (transfusion independent)
- Hemoglobin $\geq 8.0 \text{ g/dL}$ (may receive RBC transfusions)

3.2.6.2 Adequate Renal Function Defined As:

- Creatinine clearance or radioisotope GFR $\geq 70 \text{ mL/min}/1.73 \text{ m}^2$ or

- A serum creatinine based on age/gender as follows:

Age	Maximum Serum Creatinine (mg/dL)	
	Male	Female
1 to < 2 years	0.6	0.6
2 to < 6 years	0.8	0.8
6 to < 10 years	1	1
10 to < 13 years	1.2	1.2
13 to < 16 years	1.5	1.4
≥ 16 years	1.7	1.4

The threshold creatinine values in this Table were derived from the Schwartz formula for estimating GFR⁵⁰ utilizing child length and stature data published by the CDC.

3.2.6.3 Adequate Liver Function Defined As:

- Total bilirubin $\leq 1.5 \times$ upper limit of normal (ULN) for age, and
- SGOT (AST) or SGPT (ALT) < 110 U/L. For the purposes of this study the ULN for SGPT is defined as 45 U/L.
- Serum albumin > 2 g/dL

3.2.6.4 Adequate Cardiac Function Defined As:

- Shortening fraction of $\geq 27\%$ by echocardiogram, or
- Ejection fraction of $\geq 50\%$ by radionuclide angiogram.

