4.2 Therapy Delivery Map – CDX-011

Page 1 of 2

4.2.1 Therapy Delivery Map – All Cycles of CDX-011	Each cycle lasts 3 weeks (21 days). Treatment may continue for up to 14 months or 18 cycles, whichever occurs first. One cycle of treatment is described in this TDM. This TDM is on 2 pages. Use a copy of this page once for each cycle (please note cycle number below).	Patient COG ID number _____ DOB _____
---	---	--

Begin CDX-011 therapy only when ANC \geq 1000/ μ L; Platelets \geq 75,000/ μ L (transfusion independent); Hemoglobin \geq 8.0 g/dL (RBC transfusions allowed); Cr clearance or radioisotope GFR \geq 70 mL/min/1.73 m² or a serum creatinine based on age/gender as per [Section 4.2.3](#); Total bilirubin \leq 1.5 x ULN for age; SGOT (AST) or SGPT (ALT) \leq 110 U/L, and Serum albumin $>$ 2 g/dL.

DRUG	ROUTE	DOSAGE	DAY	IMPORTANT NOTES
CDX-011 (glembatumumab vedotin) IND# 128248	IV over 90 minutes	1.9 mg/kg/dose	Day 1	Recalculate the dose prior to each infusion. Round dose to the nearest 1 mg. See Section 4.2.3 for complete details.

Enter Cycle #: _____

Ht _____ cm

Wt _____ kg

BSA _____ m²

Date Due	Date Given	Day	CDX-011 ____ mg	Studies
			Enter calculated dose above and actual dose administered below	
		1	mg	a-l
		8*		(a-f)*
		21		g, h, i

Start the next cycle on Day 22 or as soon as starting criteria are met, whichever occurs later. Treatment should continue up to 14 months (or 18 cycles, whichever occurs first) in the absence of disease progression or unacceptable toxicity. If disease progression or unacceptable toxicity occurs, the patient will be taken off protocol therapy.

Note: Patients who receive surgery or radiation on any site of measurable disease prior to completion of the 6th cycle of therapy will be taken off protocol therapy.

* Cycle 1 only

See Section 5.0 for Dose Modifications for Toxicities and the COG Member website for Supportive Care Guidelines.

All Cycles

Page 2 of 2

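### Read literally, the liver entry criterion is met when only one of AST and ALT is below 110 U/L, so a marked isolated rise in the other enzyme can pass

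*Combined protocol and SAP*

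**What the plan says.** Section 3.2.6.3 gives the transaminase part of adequate liver function as "SGOT (AST) or SGPT (ALT) < 110 U/L. For the purposes of this study the ULN for SGPT is defined as 45 U/L". It stands between a bilirubin limit, which ends "upper limit of normal (ULN) for age, and", and an albumin floor of 2 g/dL. Section 3.2 states how such items are to be applied: "The eligibility criteria listed below are interpreted literally and cannot be waived".

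The therapy delivery map (4.2.1) lists the conditions for starting CDX-011 and gives the transaminase condition as "SGOT (AST) or SGPT (ALT) \leq 110 U/L". The connective is the same, but the limit is now inclusive.

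Section 3.2 also has a recheck within 48 hours before therapy, used when a post-enrollment value is out of limits or the laboratory values are more than 7 days old. The tests to repeat are "CBC with differential, bilirubin, ALT (SGPT) and serum creatinine". The consequence is stated as "If the recheck is outside the limits of eligibility, the patient may not receive protocol therapy and will be considered off protocol therapy".

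Two other provisions bear on the point. Section 3.2.5 says "Patients must have fully recovered from the acute toxic effects of all prior chemotherapy, immunotherapy, or radiotherapy prior to entering this study". Section 4.2.2 has both AST and ALT drawn before every cycle and on Day 8 of Cycle 1, with a 7-day window before Cycle 1.

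**The concern.** A liver safety limit is normally meant to bound the patient's transaminases. Joined by 'or', and read literally, this one bounds only the lower of the two. The enzyme that is abnormal has no limit of its own, at entry or in the readable start rule.

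At stake is the safety screen in a study whose Section 2.4 reports no paediatric experience with the agent. There is also a practical problem. The recheck treats ALT as informative enough to be the only transaminase repeated, yet under the 'or' a high ALT does not decide the item. Two sites with the same ALT result could reach different answers, depending on whether they look at AST or assume that ALT governs.

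**Working it through.** The plan states no figure to reproduce. The check is one of logic, with one ratio.

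**Inputs.** Limit 110 U/L and ALT ULN 45 U/L (3.2.6.3); start-rule limit 110 U/L, inclusive (4.2.1); recheck list (3.2). No ULN for AST is given in the readable text. The enzyme values below are illustrations, not trial data.

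**Step 1, scale.** The limit is 110/45 = 2.44 times the study ULN for ALT. An ALT of 300 U/L is 300/45 = 6.67 times that ULN.

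**Step 2, the criterion as written against a both-required version.**

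| AST (U/L) | ALT (U/L) | As written ('or') | Both required ('and') |
|---|---|---|---|
| 50 | 50 | met | met |
| 50 | 300 | met | not met |
| 300 | 50 | met | not met |
| 300 | 300 | not met | not met |

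The two mixed rows are the gap. In them the higher enzyme could take any value without changing the result.

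**Step 3, does the section use 'or' in this sense elsewhere?** Yes. In 3.2.6.4 the shortening-fraction item ends "by echocardiogram, or" and is followed by an ejection-fraction alternative, so either test suffices. The renal item, clearance or GFR on one side and serum creatinine on the other, works the same way. Where both tests must pass, 3.2.6.3 itself uses 'and', after bilirubin. The section's usage therefore supports the either/or reading.

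**Step 4, what else could stop the patient in row 2 at entry?**
- Bilirubin and albumin must be in range, which is compatible with an isolated transaminase rise.
- Section 3.2.5 stops the patient if the rise is an acute effect of earlier treatment that has not recovered. This narrows the gap to isolated rises of other origin.
- No readable provision requires both enzymes to be below 110 U/L.

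**Step 5, the recheck.** Suppose that only ALT is repeated. If ALT is below 110 U/L, the 'or' is satisfied and the item is met. If ALT is 300 U/L, the item is met when AST is below 110 U/L and failed otherwise. AST is not on the recheck list, and the value on file may be up to 7 days old under 4.2.2. On this item the recheck can confirm eligibility but cannot remove it by its own result.

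**Step 6, the inequality.** If both enzymes are exactly 110 U/L, the item fails in 3.2.6.3 (<) and is met in 4.2.1 (≤). The difference has little clinical weight, but the two rules should be the same.

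**The case against.** The strongest reply is that the 'or' is deliberate. The renal and cardiac items also let one of two tests suffice, and the text fits an intention that ALT should govern: a study ULN is defined only for ALT, the recheck repeats only ALT, and the end-of-therapy panel in 7.1 lists only ALT. Part of this stands. ALT may well be the intended governing enzyme, and the fix should allow for that. It does not rescue the wording. If ALT governs, row 2 of the table should fail, and as written it passes. The cardiac parallel is between two ways of testing one function, and the renal creatinine table is itself derived from a GFR formula. AST and ALT are separate results, and 4.2.2 has both drawn every time, so there is no practical need to accept either one.

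A second reply is that the gap at entry is small, given 3.2.5 and the bilirubin and albumin limits, and that a fairly recent AST will exist at Cycle 1. That stands and keeps the point minor. An appeal to site judgement does not stand, because Section 3.2 asks for a literal reading.

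A reader might go further in two directions that the documents do not support:
- **Uncapped dosing in later cycles.** The itemised start list in 4.2.3 and most of the dose modifications in 5.2 are not readable here and may limit each enzyme. The readable text also acts on toxicity during treatment: 5.1.1.2 makes most attributable Grade 3 or higher non-hematological events DLTs, and 8.1 allows removal for toxicity.
- **Weaker DLT counting.** Section 5.1.1.2 excuses some Grade 3 laboratory abnormalities that resolve to the initial eligibility criteria. It might be inferred that an isolated rise is excused at once, which would loosen the six-patient rule in 9.2. But what must resolve there is the abnormality itself, so the natural reading already looks to the affected enzyme. The documents also give no readable hepatic event rate from which an effect could be calculated.

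**Conclusion.** The concern holds as a minor wording defect. Under the literal reading that Section 3.2 demands, 3.2.6.3 and the readable start rule in 4.2.1 limit only one of the two transaminases. ALT 300 U/L with AST 50 U/L meets both. At entry the gap covers isolated rises that are not unrecovered acute effects of prior therapy. The same wording leaves the ALT-only recheck unable to exclude a patient on the transaminase item by its own result, and the two rules differ at exactly 110 U/L.

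How many patients this would affect cannot be derived from the documents. The conclusion rests on the readable text only. It makes no claim about DLT classification or probabilities, or about the unseen parts of 4.2.3 and 5.2.

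**What to change.** In 3.2.6.3 and 4.2.1, require SGOT (AST) and SGPT (ALT) each < 110 U/L, with that one inequality in both places. Add AST to the recheck list in 3.2.

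If ALT alone is meant to govern, write ALT < 110 U/L in both places instead. The recheck list then already matches and needs no change, but AST would have no limit, and the plan should make that choice openly.

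The cost is small. Both enzymes are already drawn before every cycle and on Day 8 of Cycle 1, so under the first option only the conditional recheck gains a test. A few patients with isolated rises would be excluded or have treatment delayed. Using < in 4.2.1 also means that a value of exactly 110 U/L no longer allows a start.
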